#### 4.1.5. Medical History

General medical history will be tabulated.

##### 4.1.5.1. Medical Conditions of Interest

The following medical conditions are of interest:

Categories	Medical Conditions of Interest
Endocrine	Diabetes mellitus
Liver illness	Hepatic cirrhosis
Cancer	Non-malignant tumor
Cardiac illness	Angina
	Arrhythmia
	Valvular (prosthetic aortic or mitral valves)
	Myocardial infarction
	Congestive heart failure (CHF)
Vascular illness	Peripheral vascular
	Hyperlipidemia
	Hypertension
	Cerebrovascular (stroke, transient ischemic attack)
Pulmonary illness	Asthma
	COPD
Renal illness	Chronic renal failure
	Nephrotic syndrome
Neuro-Muscular illness	Seizure disorder
	Spinal cord injury
	Parkinson's
Gastrointestinal illness	Inflammatory bowel disease (Crohn's, ulcerative colitis)
	Peptic ulcer
	Gastroesophageal reflux disease
Mental Health Diagnoses	Depression
	Anxiety
	Bipolar mood disorder

These medical conditions of interest will be tabulated per category and group.

## 4.2. SAFETY

Safety analyses will be performed on the FAS. The analysis of solicited and unsolicited AEs will be restricted to the Safety Subset, whereas for the analysis of serious AEs (SAEs) the entire FAS will be used.

Continuous variables will be summarized using the following statistics, as appropriate: number of observations, median, minimum, and maximum. Frequencies and percentages (one decimal place)

will be generated for categorical variables. No formal comparisons between groups will be provided.

Safety data will be analyzed by vaccine regimens and by risk level. Denominator for the percentages is the number of subjects in the considered population and period for a certain regimen (incidence per 100 subjects/phase) and risk level.

Solicited and unsolicited AEs accidentally captured for participants outside the Safety Subset, will be listed.

#### **4.2.1. Adverse Events (AE)**

Solicited AEs within 7-days post vaccination and unsolicited AEs within the 28-day period following the vaccination are collected only for the Safety Subset. SAE are collected for all participants.

##### **4.2.1.1. Definitions**

Solicited AEs shown in the tables and listings will be based on the overall assessment of the investigator. For unsolicited AEs, only the AEs and SAEs within the 28-day period following the vaccination will be presented in the safety tables. SAEs, will be captured and tabulated in outputs covering the whole study period. Unsolicited non-serious adverse events collected outside the 28-day period following the vaccination will be presented through listings. The number of subjects within the Safety subset will be used as a denominator for the solicited and unsolicited AEs, and the number of subjects in the FAS will be used as a denominator for the SAEs. Solicited AEs and unsolicited non-serious AEs should per protocol only be collected for the safety subset. If these would be reported by mistake for non-safety subset subjects, they will be listed separately.

Solicited local AEs will be by definition considered as related to the study vaccine.

The severity of the AEs will be classified as grade 1 to 4. The reporting of solicited AEs will be based on the investigator assessment as document in the CE domain. Solicited events of grade 0, not reported in the CE domain, will therefore not be reported in the AE analysis.

Any ARI recorded as an (S)AE in the eCRF will be excluded from any AE analysis if it is a confirmed RSV infection by RT-PCR (midturbinate swabs and sputum sample, when available) based on the central laboratory or if it is connected with a hospitalized confirmed RSV infection based on an FDA-approved RT-PCR test at the local laboratory.

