In comparison to the objectives and endpoints in the CTP, first occurrence of RT-PCR-confirmed RSV-mediated LRTD during the second, third, across the second and third and across all three RSV seasons will only be analysed according to Case Definition 1. Additionally, the efficacy endpoints will not be analysed across the first two RSV seasons, only across season 2 and 3 and across all three RSV seasons.

Following CBER comments and to align with the Phase 3 studies, the follow-up time during the RSV Seasons was updated to be defined as the time between 14 days post-vaccination and the occurrence of the first event, instead of as the time between vaccination and the occurrence of the first event. This update is not applied to the primary analysis (described in Section 3.1 and Section 4), but only to the end of efficacy study analysis (described in Section 3.6 and Section 5).

Details on the calculation of duration of an ARI episode were added to Section 4.4.2.1.3. to clarify the approach that was used during the Primary Analysis of the first RSV season. Additionally, a note was added to the description of determining a new onset or worsening to Section 4.4.2.1.1 to clarify the approach for RSV Season 2 and 3.

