**4.2.1.4. Missing Data**

Missing data (grade, relationship) will not be imputed. Subjects who do not report an event will be considered as subjects without an event. An AE with a missing severity or relationship will be considered as an AE reported, but will be considered as not reported for the severity or relationship. For example, an AE with missing severity will be considered as an AE reported for

the analysis of any grade but will be considered as not reported for the analysis of grade 3. The analysis of solicited AEs will include the safety data as documented by the investigator.

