## 5.2. SAFETY

Safety analyses for the second and third RSV season will be performed similarly to the first RSV season (see Section 4.2), based on the FAS. The analysis of solicited and unsolicited AEs will be restricted to the Revaccination Subcohorts.

For the analysis of serious AEs (SAEs) the entire FAS will be used. **For participants who will not receive a revaccination**, all SAEs will be reported from administration of study vaccine on Day 1 until the end of the first RSV season (or 6 months after vaccination, whichever comes later). In addition, SAEs classified as related to the study vaccine, SAEs resulting in death, (S)AEs resulting in study discontinuation, and (S)AEs resulting from procedures and non-investigational (concomitant) Janssen products will be collected during the entire study for all participants. For these participants, SAEs associated with ARIs and complications related to ARIs that classify as SAEs will be collected from the Day 365 (Month 12) visit until the end of the second RSV season, from the end of the second RSV season until the Day 730 (Month 24) visit, and from the Day 730 (Month 24) visit until the end of the third RSV season.

In the Revaccination Subcohorts B, C and D from 1st revaccination onwards and in Revaccination Subcohort 2A from d730 onwards, thrombosis with thrombocytopenia syndrome (TTS) is to be reported to the sponsor as an adverse event of special interest (AESI), within 24 hours of awareness. A potential AESI is defined as thrombotic events or symptomatic thrombocytopenia. For the analysis of serious AEs (SAEs) and (potential) AESIs in the Revaccination Cohorts the FAS will be used as well.

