In case the definitions of the time intervals cause overlap, the start date of the latter time interval should always start one minute after the end of the previous one.

For potential AESIs qualified for assessment, potential AESIs as identified by the investigator and potential AESIs determined programmatically, attribution to the intervals will be done similarly to the unsolicited AEs as described in Section 4.2.1.3. For Step 2 of phase allocation of adverse events, the '0 - 28 days post-dose' interval should be treated similar to 'active' periods and the rest as 'non- active' periods.

Further, for solicited AEs, the denominator for the percentages will be the number of participants with data assessed by the PI in the considered population and phase for a certain regimen (incidence per 100 participants/phase) and risk level.

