## ATTACHMENTS

### Attachment 1: Transforming Solicited AEs into Analysis Format

Solicited AEs are recorded by event and relatedness on the CE domain, similar to the format of unsolicited AEs. The reported start date of the AE on the CE domain equals the date of first occurrence of the solicited AE. The last reported date is used as the end date of the AE, regardless of possible changes in grade or time gaps also taking into account if the AE continues after Day 8. The investigators' opinion about the maximum grade over the duration of the AE will be reported. All solicited events are included on the CE domain, even when no such event occurred. In that case, the maximum grade is missing on the CE domain. These records with missing grade will not be used to construct the analysis dataset for solicited AEs. Note: Mapping of CE data to the solicited AE ADaM will occur in a similar way as unsolicited AEs are mapped in the unsolicited AE analysis database. It is possible that the investigators' assessment as captured in CE differs in grade with the diary data (recorded by day on the FA and VS domain). It is the CE data that will be used when creating ADaMs, tables and listings.

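### Day 1 solicited AE percentages are taken over the whole Safety Subset, so a participant without investigator-assessed data counts as event-free; post-revaccination percentages are taken over assessed participants only

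*SAP*

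**What the plan says.** Section 4.2 sets the general safety denominator: "Denominator for the percentages is the number of subjects in the considered population and period for a certain regimen". Section 4.2.1.1 makes it specific to the Safety Subset: "The number of subjects within the Safety subset will be used as a denominator for the solicited and unsolicited AEs". Neither sentence asks for assessed data.

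The numerator has one source. Section 4.2.1.1: "Solicited AEs shown in the tables and listings will be based on the overall assessment of the investigator". Attachment 1 explains that a solicited event that did not occur has a record on the CE domain with no grade, and then says: "These records with missing grade will not be used to construct the analysis dataset for solicited AEs".

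On missing data, Section 4.2.1.4 says: "Subjects who do not report an event will be considered as subjects without an event". The sentence does not separate solicited from unsolicited events.

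Section 5.2, for the later analyses, gives another rule for solicited AEs: "the denominator for the percentages will be the number of participants with data assessed by the PI". The same section limits its reach: "The analysis of solicited and unsolicited AEs will be restricted to the Revaccination Subcohorts".

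**The concern.** Solicited AEs are actively elicited over the 7 days after vaccination. If no investigator assessment exists, the participant's status is unknown; it is not evidence that nothing happened. Reading silence as absence is reasonable for unsolicited AEs and SAEs, which are reported when they occur. It is not reasonable for events that someone was supposed to ask about. Under the Section 4 rule an unassessed participant adds one to the denominator and can never add to the numerator, so any error is towards a lower rate.

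Solicited AE percentages are the trial's descriptive reactogenicity result. Participants in the Revaccination Subcohorts have their post-revaccination percentages computed over the assessed, so a reader who sets those beside the Day 1 percentages compares figures with different denominators.

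**Working it through.** The SAP prints no figure on this point, so there is none to reproduce. The check is direct arithmetic.

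**Inputs**
- n = 350, the planned Safety Subset per group (Section 1.2, Table 1).
- u = number without investigator-assessed solicited data. Not in the SAP; 7, 18 and 35 are assumed, so m = u/n is 2.0%, 5.1% and 10%.
- e = number with the event among the n − u assessed. Not in the SAP; set to give about 40%.

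**Formulas**
- Section 4 rate: e/n.
- Section 5.2 rate: e/(n − u).
- Possible range for the whole subset: from e/n (no unassessed participant had the event) to (e + u)/n (all had it).
- Ratio of the Section 4 rate to the Section 5.2 rate: (n − u)/n = 1 − m.

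**Results**

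| u | e | Section 4 rate | Section 5.2 rate | Possible range | Gap (points) |
|---|---|---|---|---|---|
| 7 | 137 | 137/350 = 39.1% | 137/343 = 39.9% | 39.1% to 41.1% | 0.8 |
| 18 | 133 | 133/350 = 38.0% | 133/332 = 40.1% | 38.0% to 43.1% | 2.1 |
| 35 | 126 | 126/350 = 36.0% | 126/315 = 40.0% | 36.0% to 46.0% | 4.0 |

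At m = 1% the gap is 0.40 × 0.01 = 0.4 points. At m = 0 the two rules agree. In every row the Section 4 rate is the bottom of the range.

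For scale, the 95% half-width at 40% is 1.96 × √(0.4 × 0.6/350) = 5.1 points. All three gaps are smaller, although the half-width describes random error and the gap is a one-directional shift.

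**Effect on the comparison of groups.** If m is the same in both groups, the factor 1 − m cancels and the vaccine-to-placebo ratio is unchanged. The difference shrinks by 1 − m: with assumed rates of 50% and 20% and m = 5%, from 30.0 to 30.0 × 0.95 = 28.5 points. If m differs, the ratio moves. With an assumed 10% unassessed on vaccine and 2% on placebo, a true ratio of 1.00 becomes 0.90/0.98 = 0.92.

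**The case against.** The best defence is that the two rules belong to different analyses. Section 4 covers the first season; Section 5 covers later seasons and revaccination. The assessed-only rule came with Amendment 7 in July 2022, and Section 1.6 already speaks of the season 1 primary analysis in the past tense. On this view the earlier rule was left standing for work already done and a better one was adopted going forward. No single table falls under both rules, and no re-tabulation of Day 1 solicited AEs is clearly scheduled. That stands: the two sections differ in scope and do not contradict each other.

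It can also be said that Section 4.2.1.4 never mentions unassessed participants, and that CE is designed to hold negatives as well as events, so few may be unassessed. Both are true, and m may be zero. But where a participant is unassessed, no text in Section 4.2 takes that person out of the denominator, so the effect follows even though the SAP does not spell it out.

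Finally, the assessed-only rate has an untestable assumption of its own, that the unassessed resemble the assessed. This stands too, and is the reason to print the number assessed.

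A reader might go further and fault Section 1.6 for explaining a season-specific split for follow-up time ("This update is not applied to the primary analysis (described in Section 3.1 and Section 4), but only to the end of efficacy study analysis") but not for this denominator. The documents do not support that. Several Section 1.6 entries are worded as differences from the protocol, and whether the protocol fixed a solicited AE denominator cannot be seen here, so an entry cannot be shown to have been required.

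**Conclusion.** The point holds as an optional improvement. As written, the Day 1 rule returns the lower bound of the possible solicited AE rate. The result is low by a relative m if unassessed participants resemble assessed ones, and not low at all if none of them had the event or if m = 0. The illustrated shortfall of 0.8 to 4.0 points rests on an assumed 2% to 10% unassessed and an assumed event rate near 40%.

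A reader might infer that reactogenicity has been shown to be understated, or that the vaccine-placebo comparison is biased. The SAP supports neither. It gives no missing fraction, overall or by group, and the ratio moves only if that fraction differs between groups. Section 4.2 plans no formal safety comparison, so no test or efficacy conclusion depends on this. What the text does establish is a one-directional rule for Day 1, and different denominators for Day 1 and post-revaccination percentages.

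**What to change.** - In Section 4.2.1.1, make the solicited AE denominator the number of participants with investigator-assessed solicited data, as in Section 5.2. Count them from CE before the records without a grade are dropped; otherwise assessed participants with no event would be lost. Keep the Safety Subset as denominator for unsolicited AEs.
- In Section 4.2.1.4, limit the rule that no report means no event to unsolicited AEs and SAEs.
- Show the number assessed beside each solicited AE percentage.
- Leave issued season 1 tables as the record. Where they stand, or are set beside revaccination rates, add a footnote naming their denominator.
- As a clarification only, align the remark in Section 4.2.1.1 that grade 0 events are not on CE with Attachment 1, which says that events that did not occur are recorded there.

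The cost is SAP wording, a footnote, and one re-tabulation if Day 1 solicited AEs are shown again. The downside is that Day 1 percentages become slightly higher than under the Section 4 rule and rest on the assumption that the unassessed resemble the assessed.

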### **2.3.3. Per Protocol Efficacy Population (PPE)**

The Per-protocol Efficacy (PPE) population will include all randomized and vaccinated participants excluding participants with major protocol deviations expecting to impact the efficacy outcomes. The list of major protocol deviations to be excluded from the efficacy analysis will be specified in the major protocol deviations criteria document which will be finalized before database lock and unblinding. Any participant with an RT-PCR-confirmed RSV-mediated ARI with onset within 14 days after vaccination will be excluded from the PPE population. Participants who discontinue within 14 days after vaccination will be excluded from the PPE population as well.

The PPE population is the primary efficacy population. Sensitivity efficacy analyses will also be performed on the FAS.

For exploratory efficacy analyses focusing on data from the second RSV season only, the participants of Revaccination Subcohort A will additionally be excluded. For analyses focusing on data from the third RSV season, participants of Revaccination Subcohorts A and B will be excluded. For exploratory analyses focusing on data over season two and three and over all three RSV seasons, second and third RSV season data will be excluded for the participants of Revaccination Subcohort A, and third RSV season data will be excluded for participants of Revaccination Subcohort B. Participants who develop major MPDs expecting to impact the efficacy outcomes and occurring up to the considered season will be **additionally** excluded from the PPE when focusing on data including the second or third RSV season. For exploratory analyses focusing on data over season two and three and over all three RSV seasons, only the data of the season in which the major MPDs expecting to impact the efficacy outcomes occur and the data of the seasons thereafter will be excluded. Note that in case an ARI started in RSV Season 1 or 2 and continues during Season 2 or 3 respectively, all ARI information will be considered part of the first or second year analysis, regardless if they were collected during the second or third year.

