## 3. INTERIM ANALYSIS AND DATA MONITORING COMMITTEE REVIEW

### 3.1. DATA MONITORING COMMITTEE REVIEW

The study will be formally monitored by an IDMC. In general, the IDMC will monitor safety data at regular timepoints to ensure the continuing safety of the participants. They will specifically focus on SAEs, adverse events of special interest (AESIs for subcohorts 2A, B, C and D) on

solicited and unsolicited AEs of grade 3 or higher, on unsolicited AEs (UAEs) leading to permanent discontinuation and on related UAEs. The analysis of AEs will be performed according to the specifications in Section 4.2.1. The IDMC members will be informed in case of related deaths and AESIs of study participants. In addition, the IDMC will formally monitor the efficacy endpoints at the time points specified below in the planned analysis plan.

[figure not shown]
A summary of the planned analysis is provided below, and in [Figure 1](#) (in case the study is performed in the NH only), and in [Figure 2](#) (in case the study is performed in both hemispheres).

In brief:

- If participants are only enrolled from the NH, the primary analysis will be performed at the end of the first NH RSV season, except if the incidence is exceptionally low (less than 18 observed RT-PCR-confirmed RSV-mediated lower respiratory tract disease (LRTD) events per Case Definition #2). **In that case, the independent data monitoring committee (IDMC) will perform an interim analysis (IA).** If successful, proof of concept is demonstrated. If proof of concept is not demonstrated at the IA and there is evidence for efficacy (assessed via conditional power), 2,000 new participants (Cohort 2) will be added to the study who will be vaccinated in the next NH RSV season and followed up for one RSV season. In that case, the ongoing participants (Cohort 1) will be stopped at the end of RSV season or 6 months after the last vaccination whatever comes later.

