#### 4.4.4.2. Analysis Methods

For all exploratory efficacy endpoints related to the first occurrence of a disease an exact Poisson model, as described in the primary efficacy analysis (see Section [4.4.2.2](#)) will be performed, based on the PPE population. The 95% exact 2-sided CI for the VE (1-relative risk rate) will be calculated from these regression models and graphically depicted with forest plots. In case of the model does not converge then it will be fitted with only the vaccination group as dependent variable.

For the first occurrence of complications or hospitalizations linked to any ARI and complications or hospitalizations linked to any RT-PCR confirmed RSV disease, the proportion of participants with complications and hospitalizations, will be tabulated separate and an exact Poisson model, as described in the primary efficacy analysis (see Section [4.4.2.2](#)) will be performed, based on the PPE population. The 95% 2-sided CI for the VE (1-relative risk rate) will be calculated from these regression models and graphically depicted with forest plots. In case the Poisson model for one of the above analyses does not converge, the model for the considered analysis will be fitted with only the vaccination group as independent variable.

Complications linked to any ARI and complications linked to any RT-PCR confirmed RSV disease will be summarized by System Organ Class and Preferred Term, per group and per risk level. A summary table including complications with fatal outcomes, complications reported as SAEs and those leading to permanent stop of the vaccination, will also be created. Number of participants with one complication, two complications, three complications or more than 3 complications will also be summarized.

Moreover, for the determination of oxygen saturation the number of subjects (and percentages) with baseline  $\text{SpO}_2 \geq 90\%$  and  $\text{SpO}_2 < 90\%$  during the ARI episode and the number of subjects

(and percentages) with baseline SpO2 <90 and that have a ≥2% decrease during ARI episode will be tabulated per group.

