#### 4.4.4.3. The Relationship Between the Primary Endpoints and CEC Evaluation

In order to establish the interrelationship between the primary endpoints and RT-PCR confirmed LRIs considered at least moderate by the CEC, the following analyses will be performed restricted to the placebo group. These analyses will be performed in two subgroups of the PPE set:

- participants with any RT-PCR confirmed RSV disease (see [above](#) for definition)

In each of those subgroups the following will be calculated: the percentage of subjects having an (RT-PCR confirmed RSV) ARI considered at least moderate by the CEC will be shown for:

- participants meeting Case Definition 1 versus participants not meeting any Case Definition
- participants meeting Case Definition 2 (or 1) versus participants not meeting any Case Definition
- participants meeting Case Definition 3 (or 1 or 2) versus participants not meeting any Case Definition

The corresponding odds ratio (and 95% CI) will be shown as well.

In case of limited number of participants not meeting any case definition:

- participants meeting Case Definition 1 versus participants not meeting Case Definition 1
- participants meeting Case Definition 2 (or 1) versus participants not meeting Case Definition 2 (or 1)
- participants meeting Case Definition 3 (or 1 or 2) versus participants not meeting any Case Definition

The corresponding odds ratio (and 95% CI) will be shown as well.

Moreover, the correlation between the 3 case definitions and the RT-PCR confirmed ARIs assessed by the CEC, will be explored with scatterplots.

Finally the results of the CEC evaluation will be used to explore the creation of a severity score (based on RiiQ and clinical assessment data) with a cut-off to classify an RT-PCR confirmed RSV ARI to having an RT-PCR confirmed RSV LRI assessed at least moderate by the CEC (yes/no). Classification trees (or other classification methods), logistic regression models, combinations of these or other techniques might be used to define a score. An optimal cut-off might be identified based on Receiver operating characteristic (ROC) curves, which might be used to calculate a VE.

The PPE set will be used to analyze all efficacy exploratory endpoints.

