#### 4.9.1. Analysis Methods

The PPE set will be used to analyze all clinically relevant diseases.

The proportion of participants with any RT-PCR confirmed RSV disease leading to clinically relevant diseases and those with RT-PCR-confirmed RSV-mediated LRTD based on the 3 case definitions leading to clinically relevant diseases will be tabulated per group and the corresponding VE (1-relative risk) with an exact Poisson 95% 2-sided CI will be determined and graphically depicted with a forest plot similar to the primary analysis

Depending on their occurrence, the above might be repeated for the different subcategories of clinically relevant disease (with or without calculation of VE).

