##### **4.11.1. Analysis Methods**

The PPE set will be used to analyze the medical resource utilization data.

At baseline the proportion of participants reporting having used the medical resources by category and subcategory will be summarized per group and per risk level.

For participants with any RT-PCR confirmed RSV the proportion of those reporting having used the medical resources by category and subcategory will be summarized per group and per risk level. The number of recorded visits and the length of stay will also be summarized descriptively.

In case two or more assessments are reported at the same day (for example two assessments at the same device) then the worst score per question will be used.

Finally, emerging medical resources utilized during an ARI episode will be summarized per group for all ARI cases, for all RT-PCR confirmed RSV cases, for all negative (or missing) RT-PCR RSV cases and for the 3 case definitions. A treatment - emergent medical resource is defined as a medical resource visit that was related to an ARI or a complication of an ARI (meaning the ‘Specify number of visits related to ARI or its complications’ question in the MRU is equal or larger to one).

In case a participant experiences two or more ARIs (based on the ‘Any ARI’ definition, Section 4.4.3.1) during the study then the following rules will be followed in identifying which ARIs data will be used:

- If all fulfil a case definition, then data from the RT-PCR confirmed RSV disease fulfilling the strictest definition will be used (case definition 1 > case definition 2 > case definition 3)
- If only one fulfils a case definition, then those data will be used
- If none fulfils a case definition or all fulfil the same case definition, then data from the first RT-PCR confirmed RSV disease will be used.
- If none is a RT-PCR confirmed RSV-disease, then use:
  - the ARI that fulfils the strictest case definition based on symptoms only (case definition 1 > case definition 2 > case definition 3) Or
  - the first ARI, in case 2 or more fulfil the same case definition on symptoms only or in case they do not fulfil any case definition on symptoms only.

Note: For outputs were only planned visits (ARI Day 3-5, ARI Day 29, End of season) are presented, the worst across the different scheduled and unscheduled visits will be presented per visit.

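### Confirmed RSV (S)AEs leave the AE tables while RSV hospitalisation is analysed only in the PPE, so early, non-PPE and some post-revaccination RSV illness is not identifiable as serious by arm

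*SAP*

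**What the plan says.** **AE exclusion.** Section 4.2.1.1: "Any ARI recorded as an (S)AE in the eCRF will be excluded from any AE analysis if it is a confirmed RSV infection by RT-PCR" by the central laboratory, or "if it is connected with a hospitalized confirmed RSV infection based on an FDA-approved RT-PCR test at the local laboratory". No time limit and no replacement table are given. Section 5.2 runs the later-season and revaccination safety analyses in the same way as Section 4.2.

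**Efficacy population.** Section 2.3.3: "Any participant with an RT-PCR-confirmed RSV-mediated ARI with onset within 14 days after vaccination will be excluded from the PPE population". It also removes participants with major deviations expected to affect efficacy and those who discontinue within 14 days.

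**Where the consequences of RSV illness are analysed.** For hospitalisation and complications, Section 4.4.4.2 says "the proportion of participants with complications and hospitalizations, will be tabulated separate and an exact Poisson model" will be used, on the PPE. Section 4.4.4.3 closes with "The PPE set will be used to analyze all efficacy exploratory endpoints". Section 4.9.1: "The PPE set will be used to analyze all clinically relevant diseases". Section 4.11.1: "The PPE set will be used to analyze the medical resource utilization data". Sections 5.8.1 and 5.10.1 keep the PPE for later seasons.

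**IDMC.** Section 3.1: "The analysis of AEs will be performed according to the specifications in Section 4.2.1". The same section lists 4.2, 4.4.1 and 4.4.2 as the SAP sections that apply to IDMC analyses.

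**The concern.** It is reasonable to take efficacy events out of the general AE tables, provided the efficacy tables show them. Here the two sides use different populations. The safety side removes the event from the FAS. The efficacy side reports its consequences only in the PPE. Whatever is in the FAS but outside the PPE falls between them.

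The question affected is whether vaccinees have more serious RSV illness than controls, which for an RSV vaccine is a safety question. The early post-vaccination window and the period after revaccination both bear on it. In those windows the SAE tables cannot answer it, and neither can the hospitalisation tables.

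**Working it through.** No figure in the plan is disputed, so the main check follows a serious RT-PCR-confirmed RSV ARI, recorded as an SAE, through the planned arm-level outputs.

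| Output (SAP section) | Population or rule | Onset within 14 days of Day 1 vaccination | Later onset, participant outside PPE | Subcohort A after revaccination |
|---|---|---|---|---|
| SAE tables (4.2.1, 5.2) | FAS, confirmed RSV ARI removed | absent | absent | absent |
| RSV hospitalisation, complications (4.4.4.2, 5.4.1.2) | PPE | absent | absent | absent |
| Clinically relevant disease (4.9.1, 5.8.1) | PPE | absent | absent | absent |
| Medical resource use (4.11.1, 5.10.1) | PPE | absent | absent | absent |
| Committee-rated severity (4.4.4) | PPE, first season only | absent | absent | not applicable |
| FAS sensitivity, primary endpoints (4.4.2.2) | three case definitions, from Day 1 | counted if a case definition is met; seriousness not shown | same | not applicable |
| FAS sensitivity, any RSV ARI and Case Definition 1 (5.4.1.2) | from Day 1 across three seasons | counted; seriousness not shown | counted; seriousness not shown | absent |

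**Subcohort A.** Section 1.2 continues its ARI follow-up to the end of the second season. Section 5.2 collects its SAEs from revaccination to at least that point. Section 2.3.3 excludes its second- and third-season data from the PPE analyses. Section 5.4.1.2 does the same in the FAS sensitivity analyses, where the subcohort is excluded or limited to first-season data. So the FAS counts that recover early cases elsewhere do not recover these.

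**IDMC.** Section 4.2 brings the exclusion with it. Sections 4.4.1 and 4.4.2 give case counts by case definition, including the FAS version. Hospitalisation (4.4.4) and clinically relevant disease (4.9) are not on the list.

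**Scale of the early window.** The SAP's planning figure reproduces first. Table 4 expects 9 additional events from 2,000 participants at 0.75% incidence and 70% VE:

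- 1,000 per arm: 1,000 × 0.0075 + 1,000 × 0.0075 × 0.30 = 7.5 + 2.25 = 9.75.
- 900 per arm (10% dropout, Section 4.4.1.1.1): 6.75 + 2.025 = 8.78.

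Both are close to 9. Now apply the same incidence to 2,900 per arm (Section 1.2). Two assumptions are not in the SAP: cases spread evenly over 120 to 240 days, and 5% to 20% of cases serious.

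- Placebo cases per season: 2,900 × 0.0075 = 21.75.
- Placebo onset in days 1-14: 21.75 × 14/240 = 1.27 to 21.75 × 14/120 = 2.54.
- Both arms: 1.27 × 1.30 = 1.65 (VE 70%) to 2.54 × 2 = 5.08 (VE 0% in the window).
- Serious: 0.05 × 1.65 = 0.08 to 0.20 × 5.08 = 1.02.

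**Scale of Subcohort A.** At the same incidence over one season, 240 × 0.0075 = 1.8 cases at VE 0%, or 1.8 × 0.30 = 0.54 at VE 70%. Serious: 0.05 × 0.54 = 0.03 to 0.20 × 1.8 = 0.36. Section 5 of the SAP warns that COVID-19 measures may lower these counts further.

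**The case against.** Four points count against a broader complaint.

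1. **The events are not wholly missing by arm.** A reader might infer from the exclusion and the PPE rule that RSV illness in the first 14 days is in no arm-level table. The SAP does not support that. Section 4.4.2.2 counts RSV LRTD in the FAS from Day 1 and gives numbers per group for each sensitivity analysis, and Section 5.4.1.2 does the same for any RSV ARI. An imbalance of 6 v 0 early admissions would read 0 v 0 in the hospitalisation tables, and in the SAE tables if each was recorded only as the ARI. It could still appear among the FAS case counts. This stands. Those counts do not flag seriousness, however, and comparing FAS with PPE does not isolate early cases: the FAS analysis also adds participants with deviations and positive samples that were out of stability.

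2. **Not every RSV-related SAE need be removed.** The rule names the ARI recorded as an (S)AE. Section 5.2 treats complications that qualify as SAEs as a separate item, so a separately recorded pneumonia might remain. The text does not say. It would therefore be wrong to say that all RSV-related SAEs are lost.

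3. **After 14 days, in the PPE, seriousness is well covered**: hospitalisation, a complications summary that includes fatal outcomes and SAEs, committee-rated severity and clinically relevant disease. This stands, and confines the gap in the final analysis to the windows above.

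4. **Other outputs may help.** Table shells and the IDMC Charter are separate documents. Section 4.2.1.2 plans listings or narratives as appropriate, Section 4.1.2 tabulates discontinuations by reason and group, and the IDMC is told of related deaths. None of these is specified as an arm-level count of serious RSV illness, but the unseen documents could contain one.

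**Conclusion.** The point holds as a reporting gap. As specified in the SAP, no arm-level table identifies a confirmed RSV ARI as serious, hospitalised or fatal if onset is within 14 days of the Day 1 vaccination or the participant is outside the PPE. For Subcohort A after revaccination the gap is wider, because the FAS efficacy analyses omit those data too. The SAP sections applied to the IDMC give no count of serious RSV illness by arm at any time.

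The expected size is small: about 0.1 to 1.0 serious early cases in both arms together, and at most about 0.4 per season in Subcohort A. Both rest on the SAP's planning incidence and an assumed serious fraction of 5% to 20%; the early figure also assumes even timing. Small expected counts do not close the gap, since an unexpected imbalance is what such a table is meant to reveal.

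A reader should not conclude that the primary vaccine efficacy result is affected, or that the plan ignores RSV severity in general. The conclusion rests on the SAP text alone, including the reading that Section 5.2 inherits the exclusion by referring to Section 4.2.

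**What to change.** Keep the exclusion for the general AE tables. Then:

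- Add to Sections 4.2.1.2 and 5.2 one FAS as-treated table by arm of SAEs, hospitalisations and deaths linked to an RT-PCR-confirmed RSV ARI. It should run from Day 1 onward, show onset within and after 14 days separately, and include post-revaccination periods. For Subcohort A the columns would be 1A and 2A, since both receive active vaccine at Day 365.
- Supply this table to the IDMC and name it in Section 3.1.
- State in Section 4.2.1.1 whether SAEs recorded as complications of a confirmed RSV ARI are also excluded.

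The cost is one table from data already collected, an IDMC shell update and one clarifying sentence. The drawback is that the early-window rows will probably hold few or no events, so the table is descriptive and should carry no test.
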